	
One main part of the procedure to repair a hernia involves the placement of a prosthetic (a device that substitutes for missing parts or pieces) mesh to reinforce the abdominal wall and allow for a tension free repair. The use of the mesh also helps to lower the recurrence rate (the chance that the hernia will come back). The most common type of mesh prosthesis that is placed in laparoscopic inguinal hernias is a polypropylene (the substance the mesh is composed of) mesh which has been shown to be safe and effective.
 
There is some emerging evidence that a "lighter weight" form of this mesh may improve quality of life outcomes following surgery and is the mesh currently being used at New Hanover Regional Medical Center for laparoscopic inguinal hernia repair. However, there are many different "light weight" polypropylene meshes on the market that are FDA approved and available for use. Currently, there are two different forms of the mesh being used interchangeably for the procedure at NHRMC. Both of these meshes have had good clinical outcomes.
 
The purpose of this research study is to evaluate the clinical effectiveness of the two meshes currently being used. The study may provide evidence on whether one mesh is more effective than the other. A secondary goal of the study is to evaluate the ease of use and time it takes residents to place and perform the surgery using these two different meshes. This information may make it possible to determine if one mesh is easier for residents to use during surgery and therefore take them less time to perform the procedure.
 
The effectiveness of the meshes will be measured by the patient's length of hospital stay, perioperative complications, recurrence rate, patient pain score and/or comfort level and the patient's postoperative quality of life.

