[name] will give the patients the informed consent document at New Hanover Regional Medical Center, Outpatient Surgery Clinic, SEAHEC Physicians' Office, Inpatient Surgical Units at NHRMC and/or the Emergency Department. [name] will review the page-by-page informed consent document with the patients. A copy of the informed consent document explaining the objectives and associated risks and benefits of the study will be given to the patient. The patient will be allowed to read and review the elements of the informed consent document. Patients will have a chance to ask [name] any questions they may have about the surgery and the study. If necessary, the patient will be allowed additional time to review the document. After receiving verbal consent, [name] will obtain written consent from the patient. A copy of the signed informed consent document will be given to the patient and another copy will be placed into the patient's medical record. The original document will be placed into a separate secure file cabinet that will be locked at all times.

On the day of surgery, patients agreeing to participate in the study will be randomized to receive either one of two meshes - ultrapro mesh (Ethicon) or bard 3d max (Bard). This randomization will occur with a random pattern being generated using an electronic random number generator. Then, the random assignments will be placed inside opaque, sequential envelopes. The envelopes will be opened, in order, which will guarantee a random assignment of subjects to each study arm.

Prior to the surgery, patients will be given the Carolinas Comfort Scale (CCS) and Visual Analog Scale (VAS). These study specific scales will be used to access the patients' pain and/or comfort level prior to surgery and should take no longer than 5 minutes to complete. The CCS uses a patient questionnaire of 8 questions to establish a quality measure for pain. Patients are asked to rate, on a scale of 0 to 5, sensation of mesh, pain and movement limitations during the following activities: lying down, sitting up, activities of daily living, coughing or deep breathing, walking or standing, walking up or down stairs, and while performing non-work related exercising. The VAS

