helps patients to say how good or bad their health state is. This scale uses a line with two different extremes. The extremes can vary in forms. Some VAS can ask the patient to range their pain level or current health status on a rating of either 0-10 (with 0 being no pain and 10 being the worst possible pain) or by choosing a picture of a happy or sad face.

Patients with bilateral inguinal hernias (an abnormal opening or defect that occurs on both sides of the groin), either found preoperatively or intra-operatively, will be treated as one hernia and will have the same mesh placed on both sides. Cases will be performed by one attending using his standard technique for laparoscopic inguinal hernia repair.

Data to be collected will include the patients' demographic information (age, sex, race), comorbidities (if present), smoking history, drinking history, medications, allergies and previous surgeries.

Operative data will include the following: type of anesthesia (all patients will undergo general), technique of laparoscopic access, type and side of hernia (direct or indirect), size of mesh used, type and number of tacks used to secure mesh, operative time, blood loss, urine output, and type and technique of closure.

Postoperative data will include: length of hospital stay, perioperative complications, recurrence rate, patient pain score and patient's postoperative quality of life. Further follow up data will include an assessment of the patient's recurrence rate, pain scale and quality of life during the patient's 1-2 weeks, 6 months, and 1 year follow-up. The patient will also be asked to rate their pain and/or comfort level by using the CCS and/or the VAS. During their 1-2 weeks visit, the patient will be informed of the 6 and 1 year follow-ups. For the six (6) month and one (1) year follow-up the patient will be contacted by telephone and/or be asked to return to the SEAHEC Physician's Office. The patient will not be charged for any of these services. Subjects will be tracked and identified with the use of the research record that will be set up in EPIC. Patients will be associated with the study and their surgery admission will be associated with the study for billing and coding compliance. In case the above system does not work, as a secondary system, patients will be tracked using an excel spreadsheet.

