Resident will be approached by [name] prior to the initiation of the study. [name] will give the residents the information sheet and will explain the study to the

	
residents. Additional time to review the information sheet will be provided if needed. [name] will address and answer all concerns and questions of the residents pertaining to the study. If the residents agree to participate in the study, the study coordinator will obtain verbal consent from the consenting residents. There will be no repercussions to any residents that objects to being in the study.
 
Resident level (PGY level), participation in the case (percentage of resident involvement to be determined by attending physician), time to perform the three critical portions of the case (laparoscopic access and takedown of peritoneum, placement of mesh, closure of peritoneum, and closure) will all be documented. This is routinely done by the surgical residents.
 
Following the case, the resident will be given a performance scale (NASA-TLX) to grade his/her performance in conducting the surgery. This is not routinely done but is done for some surgical cases. The NASA-TLX is a publicly available, multi-dimensional scale designed to obtain workload estimates from one or more operators while they are performing a task or immediately afterwards. It contains 6 scales that will ask the residents to rate their mental demand, physical demand, temporal demand, performance, effort and frustration on a scale of very low to very high. This will take the resident no more than three (3) minutes to complete. Once the resident has completed the scale, they will return the scale to [name]. [name] will then give the scales to the study coordinator who will keep all the scales in a locked and secure place at SEAHEC. The scale will be linked to the study patient by entering the study patient's study ID number on the scale. The residents do not routinely complete the NASA-TLX for all surgeries but for some they do. The requirement for the completion of the NASA-TLX by the surgical residents will be new and specific for this study.
 
Descriptive statistics will be performed and outcomes and resident performance will be compared based on resident level and type of mesh used. A p-value of <0.05 will be considered significant.

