
4. Inclusion/exclusion criteria: List required elements of potential subjects and those that preclude enrollment. (Exclusion criteria are not opposite of inclusion criteria, but rather elements within the already identified subject population that would be a cause for exclusion from the study.)
	
The inclusion criteria for patients in this study will include all of [name] patients undergoing laparoscopic repair for the treatment of either single or bilateral inguinal hernias from the study's approval date to December 31, 2015.
 
The inclusion criteria for residents in this study will include all surgery residents.
 
The exclusion criteria for patients in this study will include patients requiring emergency surgery, pregnant patients and patients under 18 years of age.
 
There is no exclusion criteria for residents in this study.

Part V: Financial Conflict of Interest

[figure not shown]
This section is to be completed for all financially sponsored studies.

Are you being paid to conduct this study? Yes No

If yes, complete questions below, if no skip to next section.

If financially sponsored indicate source:

Indicate by marking YES or NO if any of the financial interests or arrangements described below apply to you, your spouse, or dependent children.
		
Yes 	No 	Compensation for services (e.g. consulting fees or honoraria), or in-kind payments, other than from the Investigator's primary employer, in the prior calendar year or project over the next twelve months.
		Royalty income or the right to receive future royalties under the patent license or copyright,

		where the research is directly related to the licensed technology or work.
		Equity interests (e.g. stocks, stock options or other ownership interests, including equity holdings where the value cannot readily be determined by reference to public prices).
		Intellectual property rights (e.g. patents, copyrights, and royalties from such rights).
		Gifts or funds available to the researcher from this sponsor beyond the current research project.
		Funding expected to significantly exceed the projected costs of conducting the current research project.

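### Operative-time and portion-time comparisons pool one-sided and two-sided repairs without using the recorded side of hernia, which costs precision for mesh and leaves possible confounding by resident level

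*Combined protocol and SAP*

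**What the plan says.** The inclusion criteria (Part IV, item 4) admit patients "undergoing laparoscopic repair for the treatment of either single or bilateral inguinal hernias". Part IV, item 2 says that bilateral hernias, "either found preoperatively or intra-operatively", "will be treated as one hernia and will have the same mesh placed on both sides". The operative data in the same item include operative time and "type and side of hernia (direct or indirect"), so a side field exists, although the bracket after it describes type only.

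Time is a stated objective. Part IV, item 1 says: "A secondary goal of the study is to evaluate the ease of use and time it takes residents to place and perform the surgery". Item 2 has residents' cases timed, with "time to perform the three critical portions of the case" documented; mesh placement is one of the portions. No per-side rule is given for any of these times.

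On allocation, item 2 says "This randomization will occur with a random pattern being generated using an electronic random number generator", with sequential opaque envelopes opened on the day of surgery. No stratification is stated. The analysis paragraph at the end of item 2 names two comparison factors, resident level and mesh type, with significance at p below 0.05. Laterality is not mentioned there. Follow-up includes an "assessment of the patient's recurrence rate, pain scale and quality of life", with no explicit rule for a patient who has two repaired sides.

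**The concern.** A bilateral case places mesh on two sides, so one recorded time stands for different amounts of work in different patients. If two-sided cases take longer, the difference enters the time comparisons as unexplained variance and widens the interval for the mesh effect. A variable that could remove that variance is already on the data list but has no role in the analysis.

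The comparison by resident level is exposed in a different way. Residents are not randomised to cases. If more senior or more junior residents do a larger share of bilateral cases, the difference in time between levels partly reflects case mix, and a larger sample does not cure that. The documents do not say how cases are assigned to residents.

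For recurrence, a patient with two repaired sides has two sites at risk. The plan does not say in so many words whether failure on either side counts.

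**Working it through.** **The plan's own figure.** Planned enrolment is about 500 (Part IV, item 2), or 511 on the enrolment form (Part II, section A). No power, effect size, SD, event rate or dropout is given, so the figure cannot be reproduced.

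**Assumptions, none from the documents.**
- 1:1 allocation of 500, so 250 per arm; two-sided 0.05.
- Bilateral share p of 15-35%.
- A bilateral case adds D = 0.5, 1 or 2 within-type SDs of time, where within-type means among one-sided cases or among two-sided cases.
- A mesh effect of 0.25 within-type SD, used only as a yardstick.

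**Formulas.**
- Variance inflation from pooling: V = 1 + p(1-p)D².
- Effective sample size: 500/V.
- Power: Φ(0.25 × √(250/(2V)) - 1.96).

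**Full adjustment (V = 1).** 0.25 × √125 = 2.795, and Φ(2.795 - 1.96) = Φ(0.835) = 79.8%.

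**No adjustment.** p(1-p) is 0.1275 at 15% and 0.2275 at 35%.

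| D | p | V | Effective N | Power |
|---|---|---|---|---|
| 0.5 | 15% | 1.032 | 485 | 78.6% |
| 0.5 | 35% | 1.057 | 473 | 77.6% |
| 1 | 15% | 1.128 | 443 | 74.9% |
| 1 | 35% | 1.228 | 407 | 71.3% |
| 2 | 15% | 1.510 | 331 | 62.3% |
| 2 | 35% | 1.910 | 262 | 52.5% |

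The last row in full: V = 1 + 0.2275 × 4 = 1.910; 2.795/√1.910 = 2.022; Φ(2.022 - 1.96) = Φ(0.062) = 52.5%.

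The share of time variance due to laterality, (V - 1)/V, is 3-5% at D = 0.5, 11-19% at D = 1 and 34-48% at D = 2.

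**Recurrence.** With per-side risk r and independent sides, a bilateral patient's risk is 1 - (1 - r)². At r = 5% this is 9.75%. With p = 35% the overall risk is 0.65 × 0.05 + 0.35 × 0.0975 = 0.0666.
- Total variance: 0.0666 × 0.9334 = 0.0622.
- Variance within laterality: 0.65 × 0.05 × 0.95 + 0.35 × 0.0975 × 0.9025 = 0.0617.
- Ratio, from unrounded values: 1.008.

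At r = 1% and p = 15% the ratio is 1.001. Adjustment therefore removes less than 1% of the variance, even though a bilateral patient's risk is nearly double.

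**The case against.** The strongest reply is that this is an efficiency point on a secondary goal, sized by invented inputs. Much of that stands. Time is not among the effectiveness measures in Part IV, item 1. At 0.5 SD the loss is only one to two points of power, and the 52% figure belongs to the most extreme corner of the range. The 0.25 SD effect is not a design target of this trial, so 80% is not its planned power.

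The fix also cannot be assumed to deliver the whole gain. Some bilateral hernias are found only during surgery, and the plan does not say whether the envelope is opened before or after exploration. Laterality fixed before opening would code those cases as one-sided, so 80% is an upper limit.

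A reader might go further in several ways that the documents do not support:
- **That the mesh comparison of times is biased or invalid.** Randomisation keeps it unbiased on average. The unadjusted standard error already contains the variation from chance imbalance in bilateral share, so imbalance is not a second harm to add to the lost precision.
- **That counting a bilateral patient once is a unit-of-analysis error.** It is the sound choice, because it avoids treating two correlated sides as independent.
- **That the recurrence comparison suffers materially.** The calculation shows that it does not. The patient-level wording already points to one count per patient, and only the explicit either-side rule is missing.
- **That laterality is ignored altogether.** It is on the data list but unused in design and analysis.
- **That pain comparisons need the same adjustment.** Nothing in the documents allows that effect to be sized.

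It is also fair to say that the plan names no model for any outcome, so laterality is one of several unused variables. It still deserves a line of its own, because it changes how much work a recorded time represents, and per-side times cannot be recovered afterwards.

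**Conclusion.** The point holds for the time outcomes. Operative and portion times pool one-sided and two-sided repairs, and the recorded side is not used. The cost to the mesh comparison ranges from negligible (0.5 SD of extra time) through moderate (1 SD, equivalent to losing about 57-93 of 500 patients) to large (2 SD, about 169-238 of 500). Where this trial lies in that range depends on a bilateral share and a time difference that the documents do not give.

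For the resident-level comparison the issue is possible confounding. It is a risk to guard against, not a demonstrated bias, because the assignment of cases to residents is not described. For recurrence, only a clarifying definition is needed.

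**What to change.** - Keep one record per patient.
- Make the side field explicitly left, right or both, separate from direct or indirect type.
- Include laterality (unilateral or bilateral) as a covariate in the mesh and resident-level comparisons of operative and portion times.
- For the mesh comparison, use laterality as known before the envelope is opened, because the trial is open-label and a later finding could depend on allocation. Add a sensitivity analysis with final operative laterality.
- Record mesh-placement time for each side in bilateral cases.
- State that recurrence is counted once per patient, on either repaired side.

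The cost is one model term, a note of laterality before the envelope is opened, and one extra time entry in bilateral cases, with no added patients or visits. The gain is smaller where bilaterality is found only during surgery. The per-side timing should be settled before enrolment.

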This section is not applicable to my study

1. Where will the devices be stored?	Explain. Devices are stored in the Operation Room (OR) and are in stock in the OR holding room at New Hanover Regional Medical Center.
2. Who will receive and manage inventory for the devices throughout the study?	Name: OR Staff Title: Nurses and Doctors
3. Who will have access to the devices?	Name: OR Staff Title: Nurses and Doctors
4. How will the devices be accounted for?	Explain. Devices that are available on stock at the hospital will be used and the Lot number will be recorded.

5. What protections are in place to prevent loss or improper use?	Explain. These are devices are currently FDA approved and used on a daily basis at NHRMC so there are already precautions in place to protect them.
---	---

Part II: Study Subjects and Procedures

Complete the sections that apply to your study.

A. Subject Enrollment and Demographics:

This is a listing of the **target** study population. Check all that may apply.

You don't have to meet the anticipated subject enrollment number, but you can't exceed it without an amendment to increase the number anticipated at this site.

 Healthy Volunteers	 Chronically Ill	 Placebo (non active medicine)
 Employees	 Mentally Ill	 No Treatment Condition (control group is involved that receives no study-related treatment)
 Students	 Terminally Ill	 Storage of Specimens for Future Use
 Hospitalized Patients	 Use of Banked Specimens	 Multi-center Study: Subject Enrollment
 Male	 Use of Fetus/Fetal Tissue	# anticipated this site
 Female	 * Indigent/Uninsured	 Single Site Study: Subject Enrollment
 Adults	 * Non-English Speaking	# anticipated this site 511
 Children (under 18) (complete section V)	 * Limited or No Literacy	
 * Pregnant (see below)		

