1. Purpose and rationale: Provide a brief summary of the background information to put the study in context, include references and prior research as appropriate. State the research question(s) and tell why the study is needed or important. Describe the primary objective and any secondary objectives. Document a clear, concise purpose statement. If the study is a clinical trial involving patients as subjects and use of placebo, please justify the use of these controls.	An inguinal hernia occurs when soft tissue, which is usually part of the lower intestine, bulges through a weak point in the lower abdominal wall. The bulge that occurs from this hernia can be extremely painful and does not go away on its own. Inguinal hernia repair is one of the most common operations performed by general surgeons in the world. There are two main ways to repair an inguinal hernia, open or laparoscopic. An open repair is done by making a single long incision in the groin (the fold or hollow on either side of the front of the body where the thigh joins the abdomen) so it is possible for the surgeon to see the entire area and perform the surgery without the use of a laparoscope (an instrument through which structures within the abdomen and pelvis can be seen). Open repairs lead to more scarring and a longer recovery period. A laparoscopic repair is done by making a small cut in or just below the belly button. The abdomen is then inflated with air to allow the surgeon to be able to see all of the organs. Then, a lighted scope called a laparoscope is inserted into the incision so the surgeon can see inside the abdomen during the surgery. Surgical instruments used to repair the hernia are inserted through other small openings in the abdomen and a mesh is placed over the bulge (hernia) to reinforce the abdominal wall. Laparoscopic repair has become an accepted standard for inguinal hernia repair and has become the technique of choice for recurrent inguinal hernias.
---	---

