
2. Description of study design, methods, and procedures, describe the study in sequential order as it is to be conducted at this institution. The following should be included:
 
 ➤ type of experimental design ➤ study procedures: a sequential description of what will be asked of/done to subjects (to include identification and recruitment of subjects, consent process, treatment or intervention if applicable, length of participation, additional visits, follow-up, etc.) ➤ description and assignments of subjects to various arms of the study (if applicable) 	
This will be a prospective open-label randomized study conducted by [name] from the study's approval date to until December 31, 2015. Approximately five-hundred (500) subjects will be enrolled in this study.
 
Patients presented to NHRMC, the Outpatient Surgery Clinic, SEAHEC Physicians' Office, Inpatient Surgical Units at NHRMC and/or the Emergency Department for abdominal wall hernia repair during their pre-operative visit and who meet the inclusion and exclusion criteria will be counseled by [name] on surgical options for repair to determine if they would

- doses, frequency, and route of administration of medication and other treatment
- data that will be collected
- primary outcome measurements
- follow-up procedures
- If the study involves clinical activities, distinguish routine care procedures from those that are study specific

rather undergo an open or laparoscopic repair. If the patient is a candidate and agrees with undergoing the laparoscopic repair, they will be asked if they would like to participate in a randomized trial comparing two different meshes. If the patient agrees, he/she will be presented with information regarding this study. The study will then be explained to the patient by [name].

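### Prior repair of the operated groin is neither captured by side nor used in the analysis, which costs some precision on operative time and may confound the resident-level comparison

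*Combined protocol and SAP*

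**What the plan says.** All references are to the combined protocol and SAP.

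- **Eligibility (Part IV, item 4).** The trial enrols the investigator's "patients undergoing laparoscopic repair for the treatment of either single or bilateral inguinal hernias". The exclusions are emergency surgery, pregnancy and age under 18. Recurrent hernia is not excluded.
- **Background (Part IV, item 1).** Laparoscopic repair "has become the technique of choice for recurrent inguinal hernias". No share of recurrent cases is given.
- **Data (Part IV, item 2).** The operative items include "type and side of hernia (direct or indirect), size of mesh used, type and number of tacks used to secure mesh". The baseline list just before them includes previous surgeries as a general history item. Bilateral hernias, including those discovered during the operation, count as one hernia.
- **Randomisation (Part IV, item 2).** "This randomization will occur with a random pattern being generated using an electronic random number generator". No stratification factor is stated.
- **Analysis (Part IV, item 2).** "outcomes and resident performance will be compared based on resident level and type of mesh used". "A p-value of <0.05 will be considered significant". No covariate is named.

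**The concern.** A prior repair of the same groin is fixed before randomisation and could plausibly lengthen the operation. If such cases are enrolled and the status is not in the model, two consequences follow.

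1. **Mesh comparison of operative time.** The extra spread between first repairs and re-repairs stays in the error term, and a chance imbalance between arms goes unadjusted. Both are aspects of the same loss of precision. Neither is a bias in expectation.
2. **Resident-level comparison.** Residents are not randomised to cases. If re-repairs go more often to one training level, differences in time or workload partly reflect the cases. A larger sample does not remove that. Time and ease of use for residents are the stated secondary goal (Part IV, item 1).

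Side-specific status may be hard to recover later from a general surgical history.

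**Working it through.** The documents give no power statement, standard deviation, recurrence rate or share of recurrent cases, so there is no figure of the plan's own to reproduce. What follows sizes the loss over a range of assumptions.

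**Inputs from the documents.** "Approximately five-hundred (500) subjects will be enrolled in this study" (Part IV, item 2). The enrolment form has "anticipated this site 511" (Part II, section A); using 511 would raise the patient counts below by about 2%. The significance level is 0.05.

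**Assumptions.** 1:1 allocation (250 per arm) and a two-sided test. Share of recurrent cases r = 5% to 20%. Longer operation in recurrent cases D = 0.25, 0.5 or 1 within-group SD.

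**Step 1: operative time by mesh.** Unadjusted variance divided by adjusted variance is 1 + r(1 − r)D². The excess over 1 is the extra sample size needed if the covariate is left out.

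| r | D = 0.25 | D = 0.5 | D = 1 |
|---|---|---|---|
| 5% | 0.3% | 1.2% | 4.8% |
| 10% | 0.6% | 2.2% | 9.0% |
| 15% | 0.8% | 3.2% | 12.7% |
| 20% | 1.0% | 4.0% | 16.0% |

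Example: r = 0.15 and D = 0.5 gives 0.15 × 0.85 × 0.25 = 0.032, or about 16 of 500 patients. At D = 0.25 it is about 4 patients.

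**Step 2: the same loss as power.** For a mesh difference of 0.25 SD, power = Φ(0.25 / [√v × √(2/250)] − 1.96), where v is the ratio from step 1.
- Adjusted (v = 1): 79.8%.
- r = 10%, D = 0.5 (v = 1.0225): 78.9%.
- r = 20%, D = 1 (v = 1.16): 73.7%.

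**Step 3: chance imbalance.** The 95% range for the difference in recurrent share between arms is ±1.96 × √[r(1 − r) × 2/250]: ±3.8 points at r = 5%, ±5.3 at 10% and ±7.0 at 20%. At r = 15% it is ±6.3 points. With D = 0.5 that extreme shifts the mesh difference by 0.063 × 0.5 = 0.03 SD, against a standard error of √1.032 × √(2/250) = 0.09 SD. The unadjusted test already allows for this variation.

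**Step 4: recurrence outcome.** The ratio is pooled p(1 − p) divided by the weighted within-group p(1 − p).
- Smallest case tried: r = 5%, recurrence 2% after first repairs and 4% after re-repairs. Ratio 1.001.
- Largest case tried: r = 20%, 5% and 15%. The pooled rate is 7%; 0.07 × 0.93 = 0.0651. Within groups, 0.8 × 0.0475 + 0.2 × 0.1275 = 0.0635. Ratio 1.025.

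The loss is therefore 0.1% to 2.5%. With 250 per arm, 80% power needs differences such as 1% against 5.4%, 2% against 7.3%, or 5% against 12%. The rarity of events limits this comparison far more than pooling does.

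**Step 5: resident-level comparison.** The spurious difference is the gap in recurrent share between levels times D. If one level had 25% recurrent cases and another 5%, the gap is 0.20, giving 0.05, 0.10 or 0.20 SD for D = 0.25, 0.5 or 1. If the shares are equal it is zero. The documents do not say how cases are assigned to residents.

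**The case against.** The strongest reply is that the information is not absent. Previous surgeries are collected, and an earlier hernia repair is a previous surgery. The document is also an application summary rather than a case report form, so a form could already ask for side and procedure. This stands in part. It rules out saying that the status goes unrecorded. It does not supply a side-specific item or any use of one in the analysis.

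Three stronger readings are tempting.

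- **That a material share of cases will be re-repairs.** The background says laparoscopy is preferred when a hernia is recurrent. It does not say what share of laparoscopic cases are recurrent.
- **That adjustment is worth some 40 to 90 of the 500 patients.** The arithmetic is right for 15% recurrent and 20 to 30 extra minutes with an SD of 25: 500 × 0.1275 × 0.8² = 41 and 500 × 0.1275 × 1.2² = 92. But those are effects of 0.8 to 1.2 SD, and nothing in the documents supports choosing only large ones.
- **That pooling biases the mesh comparison or materially weakens the recurrence result.** Randomisation protects the first, and step 4 puts the second at 2.5% at most.

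It is also fair to say that confounding by resident level is conditional, and that one covariate would not make a non-randomised comparison unconfounded. It would remove one identifiable source. Finally, the lack of a named primary outcome and of a sample-size rationale in the text supplied matters more than this point.

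**Conclusion.** The point holds in a limited form. Recurrent hernias are eligible, prior repair of the operated groin is not captured explicitly or by side, and it plays no part in the analysis. The mesh comparison remains unbiased. For operative time the loss is small to moderate: about 0.3% to 4% of the sample size for effects of 0.25 to 0.5 SD, and up to 16% for 1 SD, assuming 5% to 20% recurrent cases. For recurrence it is negligible. The resident-level comparison may be confounded by case difficulty, by an amount the documents do not allow to be fixed. All shares and effects are assumptions. The point is modest and worth acting on mainly because the remedy is cheap.

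**What to change.** 1. Record prior hernia repair for each groin (left yes/no, right yes/no) from the history before the envelope is opened. Asking about both groins also covers a second side found during the operation.
2. Define one patient-level covariate: any operated side with a prior repair. This classifies bilateral patients with one first repair and one re-repair, and fits the rule that bilateral cases count as one hernia.
3. Name it in advance as a covariate in the mesh and resident-level comparisons of operative time and portion times.
4. Report recurrence by mesh and prior-repair status descriptively only. At an assumed 15% there would be about 0.15 × 250 = 37 such patients per arm, too few to compare the meshes.

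The cost is one extra form field and one model term.
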